6 STUDY TREATMENTS

6.1 Treatments Administered

All subjects in the study will receive qow (every 14 days \pm 5 days) IV SBC-103 for 156 weeks. Infusions must be administered at least 10 days apart. All study visits will be scheduled relative to Day 0. Each subject will receive 1 mg/kg for at least 12 weeks prior to consideration for a dose escalation. After evaluation of an individual subject's safety, tolerability, and PD data, a dose increase to 3 mg/kg may be implemented for that subject if the 1 mg/kg dose is well tolerated.

Subsequent modifications to the dosing schedule, or dose increases or decreases, may be considered by the Sponsor, after consultation with the PI, for each subject throughout the study based on a review of safety, tolerability, and PD data for that subject and other available safety data from the SBC-103 program.

6.1.1 Dose Adjustments

The maximum planned dose to be evaluated in this study is 3 mg/kg administered by IV infusion. In the event of poor tolerability at any time during the study the dose may be reduced or paused. If a subject cannot tolerate the lowest dose (0.3 mg/kg qow) despite measures taken to manage any IARs or other significant safety events, the subject will be discontinued from treatment. See Section 7.1.3 for guidelines for diagnosis and management of IARs and Section 6.2 for stopping rules for individual and multiple subjects.

6.1.2 Non-compliance with Study Treatment

If during the 156-week treatment period a subject misses ≥ 3 consecutive infusions, additional assessments will be required prior to resuming dosing, including safety labs (haematology, chemistry, coagulation, urinalysis and pregnancy test, where applicable), and serum and urine HS. If ≥ 6 consecutive infusions are missed, additional assessments, including lumbar puncture for CSF collection, may be required prior to resuming dosing as determined by the Sponsor in consultation with the Investigator. The next scheduled lumbar puncture would not be necessary if ≤ 2 months have elapsed since the previous lumbar puncture.

6.2 Stopping Rules

6.2.1 Stopping Rules in Individual Subjects

During the study, subjects who experience a severe IAR, an AE considered related to SBC-103, or significant elevation in specific laboratory values, will have SBC-103 dosing paused based on the rules described below.

For IARs:

• Subjects who develop a severe IAR as defined in Section 7.1.3, must stop treatment until their information is reviewed by the Sponsor and PI. Dosing with alterations to the infusion regimen (e.g., pre-treatment or slowing the rate of infusion) may resume once the Sponsor and PI approve.

• Subjects with mild or moderate IARs can continue receiving SBC-103 in the study. The Sponsor, in consultation with the PI, may recommend alterations to the infusion regimen (e.g., pre-treatment or slowing the rate of infusion).

For all other AEs (i.e., AEs that are not characterised as IARs):

- Any event considered related to SBC-103 which is either serious or severe will result in pausing additional dosing in an individual subject. The Sponsor and PI will review the data and will resume dosing only after review and agreement.
- Subjects with mild or moderate non-serious AEs can continue receiving SBC-103 in the study.

For laboratory values:

- Dosing will be paused based on confirmed elevations in ALT or AST under the following circumstances:
 - In the event that a subject's ALT or AST is $\geq 2 \times ULN$ (when baseline ALT or AST was within normal limits).
 - In the event that a subject's ALT or AST is $\ge 3 \times ULN$ (if baseline ALT or AST greater than 1.5 x ULN).

Dosing will only resume after ALT or AST have returned to baseline or to study nadir (nadir values may be confirmed by additional lab sampling at the discretion of the Investigator, using the same lab for analysis of each sample), or normalised if the baseline level was within normal limits.

When dosing is resumed it should be restarted at a reduced dose. For example, if a subject was receiving a dose of 3 mg/kg, he/she would be restarted at 1 mg/kg. If a subject was receiving a 1 mg/kg dose, he/she would be restarted at 0.3 mg/kg. In the event that the subject was receiving a dose of 0.3 mg/kg, he/she may resume at the 0.3 mg/kg dose. Dosing in an individual subject will be resumed only after ALT or AST have returned at least to baseline or to study nadir (nadir values may be confirmed by additional lab sampling at the discretion of the Investigator, using the same lab for analysis of each sample), or normalised if the baseline level was within normal limits.

If after resuming treatment at the lower dose, the ALT or AST elevation recurs at greater than or equal to 2 x ULN (for those with ALT or AST within normal limits at baseline) or 2 times the baseline value (for those with abnormal ALT or AST at baseline) study drug should be stopped and not resumed.

Dosing will also be paused based on confirmed elevations in ALT or AST with accompanying elevations in any of the following:

- Confirmed bilirubin > 1.5 x ULN.
- Confirmed INR > 1.5 .
- Eosinophilia (> 5%), rash, or fever.

If bilirubin and INR values normalise and the Sponsor and PI believes that it is safe to resume dosing, the subject may resume dosing with the dose reduced by 1 level (e.g., those previously receiving 3 mg/kg would reduce the dose to 1 mg/kg and patients receiving 1 mg/kg would reduce the dose to 0.3 mg/kg). However, in this scenario, any subject developing recurrent elevations in ALT or AST (with or without elevations in total bilirubin, INR, eosinophilia [more than 5%], rash, or fever) should not be restarted on the study drug.

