3.3.1 Decision for Continued Dosing after the First Dose in Each Subject

Due to the relatively limited experience with SBC-103 in humans (as of 30 April 2015), 24-hour in-patient safety monitoring following the first dose for each subject will be conducted in this study. The Sponsor and PI will review safety data from the first dose in each subject prior to continuation of dosing in that subject.

Page 38 of 104

ALEXION PHARMACEUTICALS, INC. PROPRIETARY AND CONFIDENTIAL: DO NOT COPY OR DISTRIBUTE WITHOUT PERMISSION FROM ALEXION

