7.1 Adverse Events and Laboratory Abnormalities

7.1.1 Clinical Adverse Events

An AE is any untoward medical occurrence in a subject, which does not necessarily have to have a causal relationship with the administration of a study drug. An AE can therefore be any unfavourable and unintended sign, symptom or disease temporally associated with the use of the study drug, whether or not considered related to the medicinal product. Pre-existing conditions that worsen in severity during the course of the study are to be reported as AEs.

All AEs occurring during the clinical study will be reported in the AE page of the CRF.

The Investigator will assess the severity, causality (relationship to study drug), and seriousness of each AE.

Severity: The Investigator will assess the severity of all AEs/SAEs as mild, moderate, or severe, based on the following definitions, developed from Clinical Data Interchange Standards Consortium Study Data Tabulation Model standard terminology v3.1.1).

- **Mild:** A type of AE that is usually transient and may require only minimal treatment or therapeutic intervention. The event does not generally interfere with usual activities of daily living.
- **Moderate:** A type of AE that is usually alleviated with additional specific therapeutic intervention. The event interferes with usual activities of daily living, causing discomfort, but poses no significant or permanent risk of harm to the research participant.
- Severe: A type of AE that interrupts usual activities of daily living, or significantly affects clinical status, or may require intensive therapeutic intervention.

Causality: AEs will be assessed as not related, unlikely related, possibly related, or related to study drug. Table 3 provides general guidance on the assessment of causality. For data reporting purposes, AEs assessed as not related or unlikely related will be classified as unrelated to study drug, and AEs assessed as possibly related or related will be classified as related to study drug. Assessment of causality should be based on the Investigator's medical judgment and the observed symptoms associated with the event.

Relationship to Study Drug	Criteria for Judgment
Related	Reasonable temporal relationship of the clinical event to study drug administration AND cannot be reasonably explained by other factors (such as the subject's clinical state, concomitant therapy, and/or other interventions).

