Possibly Related	The temporal relationship of the clinical event to study drug administration makes causal relationship possible but not unlikely AND other drugs, therapeutic interventions, or underlying conditions do not provide a sufficient explanation for the observed event.
Unlikely Related	The temporal relationship of the clinical event to study drug administration makes causal relationship unlikely but not impossible AND other drugs, therapeutic interventions, or underlying conditions provide a plausible explanation for the observed event.
Not Related	Data are available to clearly identify an alternative cause for the reaction.

Table 3:	Assessment of Causality
1 4010 01	rissessment of Causanty

Seriousness: AEs will be classified as serious or non-serious according to the definitions provided below.

An SAE is any AE that is or leads to any of the following:

- Death.
- Immediately life threatening. An AE is considered "life threatening" if, in the view of either the Investigator or Sponsor, its occurrence places the subject at immediate risk of death. It does not include an AE that, had it occurred in a more severe form, might have caused death.
- Requires in-patient hospitalisation or prolongation of existing hospitalization.
- Congenital anomaly/birth defect.
- Persistent or significant disability or incapacity.
- An important medical event that may not result in death, be life threatening, or require hospitalization may be considered an SAE when, based upon appropriate medical judgment, the event may jeopardise the subject and may require medical or surgical intervention to prevent one of the outcomes listed above.

A planned hospitalization to accommodate a study procedure is not considered an SAE. However, during the hospitalization, AEs will be collected and assessed for seriousness and reported appropriately (i.e., important medical event or prolonged hospitalization). All AEs that do not meet any of the criteria for an SAE should be regarded as *non-serious AEs*.

All SAEs and IARs must be reported to the Sponsor as described in Section 7.4.1.

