7.1.3 Adverse Events of Special Interest (Infusion-Associated Reactions)

IARs will be considered AEs of special interest. Any AE that occurs during the infusion or within 4 hours after the infusion is completed and is assessed by the Investigator as at least possibly related to study drug will be designated as an IAR. In addition, if, at any time during the study, the Investigator observes symptoms that he/she considers to be consistent with an IAR or hypersensitivity reaction related to administration of study drug, the symptoms should be recorded as an AE(s) and designated as an IAR(s). Individual AE terms should be recorded rather than the terms IAR or Infusion Associated Reaction.

As with any ERT, medications and equipment for the treatment of hypersensitivity reactions must be available for immediate use in case of unexpected, severe hypersensitivity reaction. These supplies include, but are not limited to, oxygen, antipyretics, antihistamines (e.g., diphenhydramine: parenteral and oral), corticosteroids, epinephrine, beta-adrenergic inhalers, and cardiopulmonary resuscitation devices.

General guidelines for classifying the severity of a reaction are provided in Section 7.1.1.

For similar biological products, most acute IARs occur within 2 hours of the infusion. Signs of a possible acute IAR may include:

• Hyperemia, flushing, fever and/or chills, nausea, pruritus, urticaria, gastro-intestinal symptoms (vomiting, diarrhoea, abdominal cramping), cardiopulmonary reactions, including chest pain, cardiac arrhythmias, dyspnoea, wheezing, stridor, hypotension, or hypertension.

Table 4 includes dose modifications required for all IARs and general guidance for the diagnosis and management of IARs in accordance with the institution's standard of care. The Investigator should use clinical judgement in the management of IARs in individual subjects participating in this study. In the case of a severe life-threatening reaction, current medical standards for emergency treatment are to be followed.

Symptoms	Action		

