Mild Reaction Common • Hyperemia (flushing) • Flushing • Lightheadedness • Nausea • Mild chest discomfort (tightness) Less Common • Fever and/or shivering • Palpitations • Irritability (especially in young children)	 Slow infusion rate by 50% Administer antipyretic and/or antihistamine Decrease infusion rate by a further 25% if symptoms persist If the event resolves, the infusion should continue at a reduced rate for a minimum of 30 minutes before the infusion is increased to 75% of original rate. If the subject tolerates the infusion at 75% of the original rate for at least 30 minutes the original rate may be restored for the remainder of the infusion. If reactions persist despite rate reduction, stop infusion Pre-treat with antihistamine and antipyretic prior (approximately 1.5 hours) to next infusion e.g., diphenhydramine (1 mg/kg) by mouth and acetaminophen (15 mg/kg) by mouth 		
 Moderate Reaction Hyperemia (flushing) Chest discomfort Itching and/or raised urticarial rash Severe headache Gastrointestinal symptoms, vomiting, diarrhoea, abdominal cramping 	 Stop infusion Give antihistamine IV and consider IV or oral steroids in accordance with institutional standard of care Consider giving a beta-adrenergic inhaler treatment if appropriate If the event resolves, the infusion may continue at a reduced rate of 50% of the original for a minimum of 30 minutes before the infusion is increased to 75% of the original rate. If the subject tolerates the infusion at 75% of the original rate for at least 30 minutes the original rate may be restored for the remainder of the infusion. If reaction persists despite rate reduction stop infusion Pre-treat with oral antihistamine and antipyretic prior to next infusion Collect serum for analysis of tryptase 1-3 hours after the IAR onset and another serum sample for tryptase and ADA during the next study visit (≥ 4 days after the IAR) prior to the infusion. 		

Table 4:Guidelines for the Management of Infusion-associated Reactions
(IARs)

Г

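### After the first dose, a serious infusion-associated reaction graded mild or moderate triggers no mandatory dosing hold, although any other related serious event does

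*Protocol*

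**What the plan says.** Protocol 6.2.1 has two sets of individual stopping rules for adverse events.

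- **IARs.** A severe IAR stops treatment until the sponsor and the PI have reviewed it. If the reaction is mild or moderate, the subject "can continue receiving SBC-103 in the study. The Sponsor, in consultation with the PI, may recommend alterations to the infusion regimen".
- **All other AEs.** This set is expressly confined to events not classed as IARs. It states: "Any event considered related to SBC-103 which is either serious or severe will result in pausing additional dosing in an individual subject". Its permission to continue is narrower: "Subjects with mild or moderate non-serious AEs can continue receiving SBC-103 in the study".

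Protocol 7.1.3 makes an IAR of any AE that starts during the infusion or in the following 4 hours and is judged at least possibly related. It also brings in later reactions related to study drug, "if, at any time during the study, the Investigator observes symptoms that he/she considers to be consistent with an IAR or hypersensitivity reaction".

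Protocol 7.1.1 has the investigator rate severity and seriousness separately. Severe includes an event that interrupts daily activities, "or significantly affects clinical status, or may require intensive therapeutic intervention". One criterion for a serious event is "Requires in-patient hospitalisation or prolongation of existing hospitalization".

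For the first dose only, Protocol 3.3.1 adds a compulsory step: "The Sponsor and PI will review safety data from the first dose in each subject prior to continuation of dosing in that subject".

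**The concern.** The restriction to non-serious events appears in one permission to continue and not in the other. Read as written, a related serious event loses its compulsory hold once it is classed as an IAR and graded below severe.

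Suppose a child has a possibly related, moderate reaction that leads to admission. If it starts three hours after the infusion, it is automatically an IAR and dosing can continue. If it starts five hours after and the investigator does not designate it an IAR, dosing must pause until the sponsor and PI agree to resume. Nothing in the protocol explains why the first case needs less scrutiny.

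The gap also lies where the protocol expects the hazard. Section 1.4 says most AEs with enzyme replacement are IARs. Section 1.3 reports that hypersensitivity-type signs in mice and rats mostly followed the third or fourth dose, though it cautions that animal studies do not predict human immunogenicity. Section 3.3.2 stresses multiple-dose rather than single-dose safety. At stake is whether a subject admitted with a reaction can be infused again, as early as 10 days after the previous infusion (Protocol 6.1), without anyone being required to decide that this is acceptable.

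**Working it through.** **1. The rules as a decision table.** For a related event after the first dose, the individual AE rules of Protocol 6.2.1 give:

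| Severity | Serious? | Classed as IAR | Not an IAR |
|---|---|---|---|
| Severe | yes or no | mandatory stop | mandatory pause |
| Mild or moderate | yes | **no mandatory hold** | **mandatory pause** |
| Mild or moderate | no | can continue | can continue |

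The two sets differ in exactly one row.

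**2. Can that row occur?** Severity and seriousness are separate ratings, and hospital admission makes an event serious whatever its grade. Protocol 7.2.1, on expedited reporting, refers to both serious and non-serious IARs.

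**3. Does another provision close it?**

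- *Opening sentence of 6.2.1.* It mentions related AEs but defers to the rules that follow.
- *Table 4, mild and moderate rows.* These manage the current infusion. For later doses the moderate row says "Pre-treat with oral antihistamine and antipyretic prior to next infusion" and asks for tryptase and antibody samples. It does not hold the dose. Suspension pending review appears only in the severe row.
- *Protocol 6.2.2.* Dosing stops study-wide if two subjects have a similar severe event or SAE, or one has a related life-threatening event. A single serious IAR that is not life-threatening meets neither condition.
- *Protocol 3.3.3 and 6.1.1.* Pauses and reductions are possible but discretionary.
- *Protocol 7.2.1 and 7.4.1.* The sponsor is told within 24 hours. That is reporting, not a hold.
- *Protocol 7.5.* The Safety Review Committee (SRC) reviews safety data only twice a year as routine.

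**4. How many dosing decisions are exposed?**

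- Scheduled infusions, Day 0 to Week 156 every 2 weeks: 156/2 + 1 = 79 per subject.
- Less the first, which has its own review: 79 − 1 = 78.
- Less the last, which has no following dose: 78 − 1 = 77 re-dosing decisions per subject.
- Five subjects: 5 × 77 = 385, a full-schedule maximum.

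**5. Scale under assumed rates.** The documents give no rate for serious IARs graded mild or moderate. Let p be an assumed rate per infusion, with infusions taken as independent. The expected number is 385p and the chance of at least one is 1 − (1 − p)^385.

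| Assumed p | Expected events | Chance of at least one |
|---|---|---|
| 0.01% | 0.04 | 3.8% |
| 0.05% | 0.19 | 17.5% |
| 0.1% | 0.39 | 32.0% |

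**The case against.** The strongest reply is that the gap is nearly empty. By the definition in Protocol 7.1.1, a moderate event carries no significant or permanent risk of harm, while severe covers anything that interrupts daily activities or significantly affects clinical status. An unplanned admission will often meet that. Related life-threatening events stop the study, and Table 4 places the gravest cardiac and respiratory reactions in its severe row. What is left is mainly precautionary admission. This stands as a limit on frequency, but it relies on how the grade is chosen, and the text still permits the case.

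A second reply is that IARs are an expected class effect with their own management scheme, so a narrower trigger is a reasonable choice. That supports letting non-serious reactions continue. It does not explain why a serious one needs less review than any other related serious event.

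Third, there are safeguards. This is one centre with at most five subjects, the sponsor hears within 24 hours, and the wording permits continuation without requiring it. Protocol 3.3.2 also requires a review before escalation, and SAP section 7 says all subjects were escalated. So 385 slightly overstates the decisions with no required review: crediting one per subject leaves 5 × 76 = 380. In practice a sponsor would probably pause, but the rule does not oblige it to.

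Finally, the assumed rates are unsourced, and reactions within a sensitised subject would be correlated. Both points are right: the rates show scale and do not bound the risk.

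**Conclusion.** The concern holds. From the second dose onward, no provision forces a hold after a single serious IAR that is graded mild or moderate and is not life-threatening, whereas a related serious event outside the IAR class must pause dosing. This rests on the text and on no assumed rate.

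The practical size is uncertain and probably small: up to 385 re-dosing decisions are exposed, and the 4% to 32% chance of at least one event depends entirely on the assumed 0.01% to 0.1% per infusion, independence, and a full schedule in all five subjects. It is an inexpensive improvement to a safety rule, not a flaw that undermines the study. Development of SBC-103 was stopped in July 2017 (SAP section 4), so the value now lies in correcting the rule as written and in not carrying it into another protocol.

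**What to change.** In Protocol 6.2.1, extend the mandatory IAR stop to any reaction that is severe or serious, with the same sponsor and PI review before resumption, and restrict the permission to continue to mild or moderate IARs that are non-serious. In Table 4, add to the mild and moderate rows that a serious reaction holds further dosing until the 6.2.1 review is complete.

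That is two edited bullets and two added lines. No new data are needed: the SAE/IAR form already reaches the sponsor within 24 hours, and infusions are at least 10 days apart. The cost is an occasional extra review and possibly a delayed infusion.

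One separate mismatch could be settled in the same edit: for severe reactions Table 4 requires SRC review before resumption, while 6.2.1 names the sponsor and PI.

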4.3.2 Exclusion Criteria

Subjects meeting any of the following criteria will not be eligible for participation in this study:

- Received treatment with gene therapy at any time, or any investigational drug (including high dose genistein > 150 mg/kg/day) or device intended as a treatment for MPS IIIB within 30 days prior to Screening, or is currently being treated in another study that involves an investigational drug or device.
- 2. Has any internal or non-removable external metal items that may present a safety risk for study assessments that utilise magnetic fields, or any other medical condition or

circumstance in which an MRI is contraindicated according to local institutional policy.

- 3. Previous hematopoietic stem cell or bone marrow transplant.
- 4. Known or suspected hypersensitivity to anaesthesia or the use of a sedative is contraindicated for any other reason.
- 5. History of poorly controlled seizure disorder.
- 6. A bleeding disorder, or any other medical condition or circumstance in which a lumbar puncture (for collection of CSF) is contraindicated according to local institutional policy.
- 7. Known hypersensitivity to eggs. Subjects at high risk for food allergy that may include eggs should be tested according to local guidelines.
- 8. Other medical conditions or comorbidities (e.g., alanine aminotransferase [ALT] or aspartate aminotransferase [AST] > 3 x the upper limit of normal [ULN], confirmed by repeat testing, analysed locally and based on the standardised reference range provided in the laboratory manual), or other markers of clinically significant liver dysfunction (e.g. elevated bilirubin, [with the exception of subjects with confirmed Gilbert's disease] confirmed by repeat testing, or elevated prothrombin time [PT]/international normalised ratio [INR] confirmed by repeat testing analysed locally and based on the standardised reference range provided in the laboratory manual) which in the opinion of the Investigator, in consultation with the Sponsor, would interfere with study compliance, or confound data interpretation.

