5.2 Clinical Laboratory Assessments

5.2.1 Routine Assessments and Biomarkers

A list of all clinical laboratory tests that will be performed is provided in Table 1; the time points for sample collection are specified in the SOA.

Blood collected for standard haematology and serum chemistry (including coagulation parameters) will be analysed locally.

During Screening, if a subject's ALT or AST is greater than 3 x ULN, or a subject has elevated bilirubin or PT/INR, confirmatory testing will be completed. Abnormal safety labs at Screening can be repeated within 1 to 2 weeks. The difference between these 2 pre-treatment values for each abnormal laboratory parameter should differ by < 20% for each subject.

Efforts should be made by the Investigator to review subject medical history, concomitant medications and health status so that a clear explanation for the elevation is established. The Investigator, in consultation with the Sponsor, shall make a determination of subject eligibility based on review of Exclusion Criterion 8.

During the study, after treatment with SBC-103, in the event that a subject's ALT or AST is 2 x ULN (when baseline ALT or AST was within normal limits) or 3 x ULN (when baseline ALT or AST was greater than 1.5 x ULN), or when a subject has an elevation in bilirubin or PT/INR a confirmatory test should be completed at the earliest possible time point, but not later than the next scheduled visit. Upon positive confirmation of the elevated transaminases as described above, dosing will be paused until AST and ALT have returned to baseline or to study nadir (nadir values may be confirmed by additional laboratory sampling at the discretion of the Investigator, using the same laboratory for analysis of each sample), or normalised if the baseline level was within normal limits. See Section 6.2 for stopping rules.

Every effort will be made to collect urine for urinalysis testing. If urine can be collected, a urine pregnancy test will be performed and analysed locally for females of child-bearing potential. If a urine sample is not able to be provided, a serum pregnancy test will be performed and analysed locally.

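### The ALT/AST stopping rule sets no isolated trigger for baselines above ULN and up to 1.5 x ULN, and Section 6.2.1 and Table 4 name different approvers for restart after a severe IAR

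*Protocol*

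**What the plan says.** **Transaminases.** Protocol 6.2.1 pauses dosing for a confirmed ALT or AST of at least 2 x ULN "when baseline ALT or AST was within normal limits", and of at least 3 x ULN "if baseline ALT or AST greater than 1.5 x ULN". Section 5.2.1 uses the same two baseline groups for the confirmatory test, the second being "3 x ULN (when baseline ALT or AST was greater than 1.5 x ULN".

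Two further rules stand in 6.2.1. The combined rule begins "Dosing will also be paused based on confirmed elevations in ALT or AST with accompanying elevations in any of the following" and lists bilirubin, INR, eosinophilia, rash and fever. The recurrence rule, which applies after a restart, uses 2 x ULN for normal baselines and "2 times the baseline value (for those with abnormal ALT or AST at baseline").

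Exclusion criterion 8 (4.3.2) gives as its example ALT or "aspartate aminotransferase [AST] > 3 x the upper limit of normal [ULN], confirmed by repeat testing", and qualifies its list with "which in the opinion of the Investigator, in consultation with the Sponsor, would interfere with study compliance, or confound data interpretation".

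**Severe IAR.** Section 6.2.1 has the Sponsor and PI review the case and approve resumption. Table 4 in 7.1.3 suspends the subject until the SRC has reviewed the reaction, and makes restart depend on SRC approval.

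**Smaller points.** For restart, 5.2.1 requires both AST and ALT to have recovered; 6.2.1 joins the two enzymes with or. Footnote 3 to the schedule of assessments (Protocol 14.1, repeated in SAP 9.1) calls for local ranges for locally analysed samples and also for central ranges throughout. Exclusion 8 is "based on the standardised reference range provided in the laboratory manual".

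**The concern.** Safety and tolerability is the primary endpoint, and Protocol 3.2 cites stopping rules for IARs and liver enzymes as protections. A subject whose baseline falls between the two groups can have an isolated transaminase rise with no automatic confirmatory test and no automatic pause.

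After Week 28 the scheduled chemistry draws are 8 weeks apart, or 10 (for example Week 68 to Week 78). Draws are pre-dose and dosing is every 2 weeks, so 8/2 = 4 or 10/2 = 5 infusions fall between draws. When a trigger fires, by contrast, the repeat test is due no later than the next visit. The liver is a relevant organ: Section 1.3 reports that it took up the major fraction of the dose in rat and monkey, with minimal to mild liver inflammation in rats at all doses.

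For a severe IAR, following the 6.2.1 bullet alone would allow dosing to restart without the independent review that Table 4 requires.

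**Working it through.** The plan states no figure here to reproduce. The check enumerates the rule and compares the texts.

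**Step 1: classes.** Express each baseline in x ULN: N, within normal limits (example 0.9); B, above 1.0 and up to 1.5 (example 1.3); H, above 1.5 (example 2.5). Two enzymes in three classes give 3 x 3 = 9 pairings.

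**Step 2: apply the rule both ways.** Literal reading: either enzyme can satisfy the baseline condition. Alternative: each enzyme is judged by its own baseline.

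| Baseline ALT / AST | Literal: lowest trigger (x ULN) | By enzyme: ALT; AST |
|---|---|---|
| N / N | 2.0 | 2.0; 2.0 |
| N / B | 2.0 | 2.0; none |
| N / H | 2.0 (3.0 also applies) | 2.0; 3.0 |
| B / N | 2.0 | none; 2.0 |
| B / B | none | none; none |
| B / H | 3.0 | none; 3.0 |
| H / N | 2.0 (3.0 also applies) | 3.0; 2.0 |
| H / B | 3.0 | 3.0; none |
| H / H | 3.0 | 3.0; 3.0 |

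Literal reading: 1 of 9 has no isolated trigger (B/B). By enzyme: 5 of 9 leave at least one enzyme without one (N/B, B/N, B/B, B/H, H/B). At the edges, a baseline of exactly 1.0 has the 2 x ULN line, anything from just above 1.0 through 1.5 has none, and just above 1.5 has the 3 x ULN line.

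**Step 3: the literal reading is not a clean rescue.** With ALT normal and baseline AST 2.5 x ULN, an unchanged AST already meets the 2 x ULN line, since 2.5 >= 2.0.

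**Step 4: do other provisions supply the missing first trigger?**
- Combined rule (6.2.1): mandatory with no minimum ALT/AST multiple, but it needs an accompanying sign.
- Recurrence rule (6.2.1): applies only after a pause and restart.
- Related serious or severe AE rule (6.2.1): needs such an event. Under 7.1.2 an out-of-range value is not an AE unless judged clinically significant.
- Repeat testing and hepatologist review (7.2.4): depend on judgement.
- Requested pause (3.3.3): discretionary.

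None is an automatic first trigger for an isolated rise.

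**Step 5: candidate trigger for the band, 2 x baseline.** 1.1 gives 2.2; 1.3 gives 2.6; 1.5 gives 3.0. The limits 2 x 1.0 = 2.0 and 2 x 1.5 = 3.0 meet the existing lines without a jump. Just above the band, the present line is a 3.0/1.51 = 1.99-fold rise. Above 1.5, 2 x baseline would loosen the rule (baseline 2.0: 4.0 against 3.0), so 3 x ULN stays there. Applied by enzyme, 0 of 9 pairings then lack a trigger.

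**Step 6: severe IAR, side by side.**

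| Place | Who decides | Covers a single severe IAR? |
|---|---|---|
| 6.2.1 | Sponsor and PI | Yes |
| Table 4 (7.1.3) | SRC | Yes; 7.1.3 says its dose modifications are required for every IAR |
| 6.2.2 | SRC and Sponsor | Only two subjects with similar severe events or SAEs, or one life-threatening AE at least possibly related |
| 3.3.3 | SRC, Sponsor and PI | Written for requested pauses |
| 7.5 | SRC, advisory | Available for consultation |

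Section 6.2.1 points to 7.1.3, and Table 4 points back to 6.2, so the cross-references do not settle which text governs. The third Table 4 row has no legible label in the text available here; its position after mild and moderate, and its content (anaphylactic shock, laryngeal oedema, epinephrine), identify it as the severe row.

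**The case against.** The strongest reply is that little is missing. On the literal reading only one pairing in nine lacks a trigger, the study has at most 5 subjects at one centre, and several protections remain, one of them mandatory when another sign accompanies the rise. That stands as a limit on size, but it does not supply the number.

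The example in step 3 can also be called strained: the rule speaks of confirmed elevations and allows restart at baseline, so an unchanged value is hardly its target. That is a fair reading of intent, but the text does not state it.

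The proposed fix leaves a similar weakness higher up. With 3 x ULN kept above 1.5, a baseline of 2.9 triggers at 3.0/2.9 = 1.03-fold, and a subject enrolled at 3.2 would already meet the line. This is true, but it belongs to the existing rule for high baselines and errs towards pausing.

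On the IAR, the two texts can be applied together: 6.2.1 is permissive, it already requires Sponsor approval, and every IAR reaches the Sponsor within 24 hours. The SRC charter, which is not available here, may also help. This shows overlapping requirements rather than outright contradiction; 6.2.1 still does not say that SRC approval is needed.

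Finally, the laboratory manual's range in exclusion 8 might be the central range, which cannot be checked. The conflict within footnote 3 does not depend on it.

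**Conclusion.** The concern holds. Sections 5.2.1 and 6.2.1 give no isolated ALT/AST trigger when both baselines are above ULN and up to 1.5 x ULN, or when either is, if enzymes are judged separately: 1 or 5 of the 9 pairings. For a single severe IAR not caught by 6.2.2, 6.2.1 and Table 4 name different approvers and no other section resolves it.

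The counts carry no probability. No baseline values are given, so whether any subject falls in the band is unknown. SAP Section 4 records that development stopped in July 2017, and SAP 4.1.4 presents laboratory data as listings only, so the consequence lies in subject protection and in the range behind the high/low flags (SAP 7.3.3.1), not in any summary statistic. It is worth correcting because safety is the primary endpoint and the correction is cheap.

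**What to change.** 1. In 5.2.1 and 6.2.1, judge each enzyme by its own baseline: within normal limits, at least 2 x ULN; above 1.0 and up to 1.5 x ULN, at least 2 x baseline (the multiple the recurrence rule already uses); above 1.5 x ULN, at least 3 x ULN as now. State that the recurrence rule is read the same way.
2. In 6.2.1, add that resumption after a severe IAR also needs SRC review and approval, as in Table 4.
3. Minor: require both ALT and AST to have recovered before restart, in 5.2.1 and in both places in 6.2.1.
4. Minor: name one reference-range source in footnote 3, in the Protocol and SAP copies, for the x ULN triggers and the high/low flags.

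Cost: a protocol wording amendment, with IRB/IEC approval if applicable; an occasional extra confirmatory test; one line in the SAP; and an ad hoc SRC review by compensated members after a severe IAR, which Table 4 already requires. No added subjects or scheduled visits.
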